8.1.2 Vision-threatening complications

Vision-threatening complications are defined as occurrence of any of the following adverse events:

- PDR
- Any ocular neo-vascularization

09 FEB 2023 Page: 51 of 95

- Center-involved (ci) (central ETDRS subfield) DME
- Drop of BCVA of 10 letters or more from baseline

The assessment will be continued after treatment discontinuation if possible.

Treatment of the vision threatening complication should follow local standards and guidelines, i.e. treatment of ci DME with anti-VEGF or other appropriate measures, at the discretion of the investigator.

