9.4.2 Primary endpoint

The primary endpoint is "≥ 2-step improvement in DRSS at 48 weeks of treatment in the study eye".

Missing data for this endpoint will be imputed using the last measured DRSS score prior to this

If the last measured DRSS score already showed an improvement by ≥ 2 steps at the last measurement prior to the missing assessment, the participant will be considered a responder for the primary endpoint. Otherwise, the participant will be considered a non-responder.

Participants that had a vision-threatening complication as defined in Section 8.1.2 prior to the missing assessment will be considered non-responders.

The primary analysis will be conducted using a Bayesian framework. This decision depends upon the following criteria:

- (a) there is \geq 90% posterior probability for superiority vs placebo and
- (b) if there is \geq 50% posterior probability that the proportion of patients with DRSS \geq 2-step improvement exceeds 25%.

The response criterion is assumed to be binomially distributed within each treatment arm. For the Bayesian evaluation, a Jeffries' prior (i.e. a Beta (0.5;0.5)-prior) will be used. Under these assumptions, the posterior distribution for the parameter π will be a Beta (k+0.5,n-k+0.5)-distribution, where

- k is the number of patients with DRSS \geq 2step improvement within the respective study arm and
- n is the number of participants within the respective study arms.

In order to demonstrate criterion (a), the posterior distribution of $\pi_{ACT} - \pi_{PLC}$ will be used to establish the posterior probability that $\pi_{ACT} - \pi_{PLC} > 0$ (e.g. by using a Monte-Carloapproach).

The posterior distribution for criterion (b) can be directly evaluated from the Beta (k+0.5,n-k+0.5)- distribution in the runcaciguat arm.

This primary analysis will be conducted on the PPS. A sensitivity analysis will be performed on the FAS. Further sensitivity analyses will include a separate analysis for each runcaciguat dose level that was reached during titration (on the PPS), as well as an analysis in the subpopulation of participants without major changes in vital signs (i.e. systolic blood pressure and pulse rate). Another sensitivity analysis will be conducted using multiple imputations for missing data. This analysis will be described in the SAP in a more detailed way.

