#### Intercurrent events:

- Dropout due to a VTC in the study eye: *composite variable strategy* (analyze study participant as non-responder)
- Dropout ...

... before Visit 9 (week 12) composite variable strategy (analyze study participant as non-responder)

... after Visit 9 (week 12) with EoT DRSS assessment performed within 4 weeks of treatment discontinuation

while on treatment strategy (use the last available DRSS assessment (LOCF)

... after Visit 9 (week 12) with EoT DRSS assessment performed more than 4 weeks after treatment discontinuation

*while on treatment strategy* (use the last available DRSS assessment prior to treatment discontinuation (LOCF))

• Non-compliance with study intervention, defined as actual drug intake lower than 80% or higher than 120% of the planned drug intake per protocol: *principal stratum strategy* (exclusion from analysis, as an adequate imputation of response information is considered not possible)

The secondary estimand (analysis on FAS) is identical to the primary estimand (analysis on PPS) with the exception that the condition relating to compliance is not included.

Version 3.0

The other estimand (analysis on PPS) is defined below:

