#### **Intercurrent events:**

- Dropout due to a VTC in the study eye: *composite variable strategy* (analyze study participant as non-responder)
- Missing DRSS assessment on Visit 15 (week 48) due to early discontinuation: *hypothetical strategy* (multiple imputations will be performed for the responder criterium)
- Non-compliance with study intervention, defined as actual drug intake lower than 80% or higher than 120% of the planned drug intake per protocol: *principal stratum strategy* (exclusion from analysis, as an adequate imputation of response information is considered not possible)

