#### 4.1.4 Discontinuations

Participants who discontinue the study prematurely (i.e., dropout) will not be replaced. A temporary discontinuation exceeding 14 consecutive days or 21 days overall results in a permanent discontinuation. If unexpectedly high dropout rates occur (e.g., due to COVID-19), the number of randomized participants may be increased by up to 20%. For further details with respect to the analysis of dropouts refer to the Section 4.1.3 on handling of Missing Data.

A participant may withdraw from the study at any time at his/her own request or may be withdrawn at any time at the discretion of the investigator for safety, behavioral, or compliance reasons. This includes cases where, in the investigator's opinion, continued participation in the study would be harmful to the participant's well-being. This is expected to be uncommon. At the time of discontinuing from the study, if possible (if the participant is not lost to follow-up and if the health status of the participant allows), Visit 15 should be conducted as early discontinuation visit, followed by safety follow-up (Visit 16). Data collected at early discontinuation visits will be handled as follows: If a valid DRSS assessment is available from the early discontinuation visit, this value will be considered for analyses for the respective visit. Other variables assessed at early discontinuation visits will be listed for individual follow-up but not be considered for summary statistics.

Participants who permanently discontinue study treatment are invited to continue to attend all protocol-specified study visits. Values assessed at visits after discontinuation from study treatment will be listed for individual follow-up but not be considered for summary statistics. All values assessed after study treatment discontinuation will be flagged in the listings.

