## 4.2.2 Main Analytical Approach

For the primary analysis, the last observation before missing DRSS values will be carried forward (LOCF) to impute missing values if the participant dropped out after visit 9 (week 12) and the EoT DRSS assessment was performed within 4 weeks of treatment discontinuation (*while on treatment strategy*). If the last measured DRSS score already showed an improvement by  $\geq 2$  steps at the last measurement prior to the missing assessment, the participant will be considered a responder for the primary endpoint. Otherwise, the participant will be considered a non-responder. If the participant dropped out after visit 9 (week 12) and the EoT DRSS assessment was performed more than 4 weeks after treatment discontinuation the last available DRSS assessment prior to treatment discontinuation will be used (LOCF) (*while on treatment strategy*). Participants who dropped out before visit 9 (week 12), or who had a VTC in the study eye prior to the missing assessment will be considered non-responders regardless of the DRSS level (*composite variable strategy*).

Treatment groups will be runcaciguat and placebo, actually administered dose levels will not be considered for this analysis.

Primary efficacy analyses will be performed on the PPS and will include only study intervention compliant participants (*principal stratum strategy*). In addition, sensitivity analyses will be performed on the FAS. Further analyses may include a separate analysis for each runcaciguat maintenance dose level that was reached during titration (on the PPS). Participants will be analyzed according to the treatment (i.e., runcaciguat or placebo) they actually received.

The study will be analyzed using Bayesian inference with non-informative priors. PoC shall be defined as fulfillment of the following criteria:

•  $P(\pi_{ACT} - \pi_{PLC} > 0 | data) \ge 0.9$ i.e., the posterior probability that the difference between  $\pi_{ACT}$  and  $\pi_{PLC}$  is greater than 0 (clinical activity) given the data observed in the study needs to be 90% or more,

and

•  $P(\pi_{ACT} > 0.25 | data) \ge 0.5$ i.e., the posterior probability that  $\pi_{ACT}$  is greater than 0.25 (clinical relevance) given the data observed in the study needs to be 50% or more.

95% credible intervals will also be presented for  $\pi_{ACT}$  and for  $\pi_{PLC}$ 

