## 4.2.3 Sensitivity Analysis

For the sensitivity analysis, a multiple imputation with 100 repetitions will be performed to receive the responder criterium for participants with missing DRSS assessment on Visit 15 (week 48) due to early discontinuation (*hypothetical strategy*). The imputation model used to generate complete data sets will be a logistic regression for the responder criterium with stratum (baseline DRSS) and treatment group as effects. To use the regression method, the pattern of missingness need to be monotone.

Participants who had a VTC in the study eye prior to the missing assessment will be considered non-responders regardless of the DRSS level (*composite variable strategy*).

Treatment groups will be runcaciguat and placebo, actually administered dose levels will not be considered for this analysis.

The analyses will be performed on the PPS and will include only study intervention compliant participants (*principal stratum strategy*).

The analysis using Bayesian inference with non-informative priors, as described in the section above, will be repeated on the complete data sets obtained from the multiple imputation.

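### A study eye given anti-VEGF for a vision-threatening complication, kept on study drug and graded at Week 48 is scored on that grade, because the complication counts as non-response only when the assessment is missing or the participant drops out

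*SAP*

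**What the plan says.** Three passages make a VTC a non-response, and all three depend on a missing grade.

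- SAP 4.2.2 (primary analysis): participants "who had a VTC in the study eye prior to the missing assessment will be considered non-responders regardless of the DRSS level".
- SAP 4.2.3 (multiple imputation): "Participants who had a VTC in the study eye prior to the missing assessment will be considered non-responders regardless of the DRSS level".
- Protocol 9.4.2: "Participants that had a vision-threatening complication as defined in Section 8.1.2 prior to the missing assessment will be considered non-responders".

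In SAP 1.1 the primary estimand lists "Dropout due to a VTC in the study eye" as a composite event. The estimand labelled 'other' repeats this and adds "Missing DRSS assessment on Visit 15 (week 48) due to early discontinuation". The FAS estimand differs from the primary one only in dropping the compliance condition. None of them names rescue treatment.

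On management, Protocol 8.1.2 says: "Treatment of the vision threatening complication should follow local standards and guidelines, i.e. treatment of ci DME with anti-VEGF or other appropriate measures". Protocol 7.1.1 lists a VTC or progression to PDR among the reasons for which study drug may, not must, be stopped, and the Amendment 4 rationale says that stopping is not mandatory. Protocol 1.1 and SAP 1.2 instead describe treatment as continuing until a VTC or PDR develops.

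**The concern.** A participant who has center-involved DME in the study eye, receives anti-VEGF and stays on study drug has an observed Week 48 grade, so no VTC rule applies and the grade is scored. The same complication and rescue give non-response if Week 48 is missed and possibly response if it is attended. Protocol 4.2 states that intravitreal anti-VEGF produced 2-step DRSS improvement from 8 weeks at the earliest, with a maximum at 6 to 12 months. The plan can therefore credit the effect of rescue to the randomized arm.

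Equal rescue in both arms does not remove the problem. The activity criterion compares the arms, but the relevance criterion is an absolute bar of 25% on the active arm, and rescue responders in that arm help to clear it.

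**Working it through.** **1. Which route is realistic.** Table 6-1 in SAP 6.6 has no DME item, so DME does not by itself raise the level. Levels 47, 53 and 61 are steps 5, 6 and 7, and a 2-step response needs step 3 (baseline 47) or step 4 (baseline 53). An eye at level 61 would have to fall 7 − 3 = 4 or 7 − 4 = 3 steps, and the SAP version history calls a return from PDR to NPDR extremely unlikely. Rescue of PDR is therefore set aside; DME is the route.

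**2. Is there time.** In the schedule of activities Visits 12, 13, 14 and 15 fall on days 169, 225, 281 and 337. DME found at Visit 14 leaves 337 − 281 = 56 days, only the earliest effect, and the ±7-day windows can shorten it. Visit 13 leaves 337 − 225 = 112 days and Visit 12 leaves 337 − 169 = 168 days. DME rescued well before Visit 15 is the main case.

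**3. The plan's own figure.** Inputs from Protocol 9.2 and SAP 4.2.2 and 5: 40 evaluable per arm, rates 35% v 10%, prior Beta(0.5, 0.5), posterior Beta(k + 0.5, n − k + 0.5). PoC needs P(π_ACT > π_PLC) ≥ 0.90 and P(π_ACT > 0.25) ≥ 0.50. Exact enumeration over both binomial counts gives 0.903, in agreement with the stated 90% or more.

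**4. The boundary.** With 9 of 40 active responders P(π_ACT > 0.25) = 0.368 (fail); with 10 of 40 it is 0.512 (pass). The chance that PoC is met but would be lost with one active responder fewer is 0.066 at 35% v 10% and 0.096 at 20% v 10%.

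**5. Size.** The documents give no VTC rate, rescue rate or post-rescue response rate, so all three are covered by assumption. Let a share v of eyes be rescued on drug in each arm, let a share q of these be graded as responders, and let other eyes keep the base rate p.

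- As written: arm rate = (1 − v)p + vq.
- Rescue counted as non-response: arm rate = (1 − v)p.

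Example, v = 5%, q = 50%, 20% v 10%: as written 0.95 × 0.20 + 0.05 × 0.50 = 0.215 and 0.95 × 0.10 + 0.025 = 0.120; with rescue as non-response 0.190 and 0.095.

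P(PoC), 40 per arm:

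| True rates | v | As written, q = 20% | As written, q = 50% | Rescue = non-response |
|---|---|---|---|---|
| 10% v 10% | 5% | 0.006 | 0.013 | 0.003 |
| 10% v 10% | 10% | 0.008 | 0.027 | 0.002 |
| 20% v 10% | 5% | 0.230 | 0.280 | 0.194 |
| 20% v 10% | 10% | 0.223 | 0.308 | 0.155 |
| 35% v 10% | 5% | 0.879 | 0.884 | 0.870 |
| 35% v 10% | 10% | 0.851 | 0.852 | 0.826 |

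With no rescue the three values are 0.004, 0.236 and 0.903. At 35% v 10% the proposed rule costs 0.879 − 0.870 = 0.009 to 0.884 − 0.870 = 0.014 at v = 5%, and 0.025 to 0.026 at v = 10% (0.029 at q = 30%, where the as-written value is 0.855). The activity criterion alone passes at about 0.10 when both rates are 10%.

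**The case against.** **Reach into the primary analysis.** The primary analysis runs on the PPS, and SAP 3 leaves validity findings to the ACIR document, which is not available here. It may exclude participants given anti-VEGF. This stands: a reader might infer that the PoC decision is certainly affected, and the documents do not show that. Exclusion from the PPS would still not be non-response and would leave the FAS analysis as it is.

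**Treatment may stop at a VTC.** Protocol 1.1 and SAP 1.2 say so. If that text governed, the case would largely disappear. Protocol 7.1.1, deliberately changed by Amendment 4, says otherwise, so the passages conflict.

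**Those who stop drug may already be covered.** SAP 4.1.4 equates dropout with leaving the study ("Participants who discontinue the study prematurely (i.e., dropout) will not be replaced"), but SAP 1.1 and 4.2.2 subdivide dropout by time since treatment discontinuation. On the second reading, stopping drug because of a VTC is already composite non-response. SAP 4.1.4 also says: "Values assessed at visits after discontinuation from study treatment will be listed for individual follow-up but not be considered for summary statistics". A reader might infer that every rescued eye is scored on its late grade; that is clear only for participants who stay on drug.

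**The size depends on the assumed response after rescue.** This stands. With v = 5% and q = 20%, P(PoC) at 20% v 10% is 0.230, hardly different from 0.236 with no rescue.

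**Conclusion.** The gap is real and should be closed before unmasking, but its size is conditional. It concerns study eyes with a VTC, in practice center-involved DME, that are rescued, stay on study drug and have a Week 48 grade. A reader might suppose that such eyes are few, or many; the documents support neither, and the number is unknown.

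Under the stated assumptions (40 per arm, equal rescue of 5% or 10%, response after rescue 20% to 50%), the choice of rule moves P(PoC) at 20% v 10% by 0.230 − 0.194 = 0.036 up to 0.308 − 0.155 = 0.153. These are differences between two ways of scoring rescue, not a measured bias. A reader might also infer a serious false-positive problem. That is not supported: false PoC stays at 0.027 or less, well below the roughly 0.10 of the activity criterion alone. What weakens is the extra protection from the relevance criterion, where one active responder can decide the result. Unequal rescue was not covered in the table; more rescue on placebo would work against showing activity.

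**What to change.** In SAP 1.1, 4.2.2 and 4.2.3, before unmasking:

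- Add one intercurrent event: anti-VEGF (intravitreal in the study eye, or systemic), or intraocular steroid, laser/PRP or vitrectomy in the study eye, started after randomization and before the DRSS assessment. Handle it as composite non-response whether or not the grade is observed, in the PPS, FAS and multiple-imputation analyses. Systemic anti-VEGF is included because exclusion criterion 22 names it. This extends the composite strategy that the SAP already uses for a VTC before a missing grade.
- Add one sensitivity analysis in which any study-eye VTC before the assessment is non-response, and report rescued eyes per arm.
- Define dropout once, as leaving the study or as stopping drug.
- Reconcile Protocol 1.1 and SAP 1.2 with Protocol 7.1.1 on whether treatment continues after a VTC. No clinical rule is proposed here.

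First confirm in masked data that the derivation is possible. Protocol 6.8 records drug, route and indication, but no passage describes a record of the treated eye, laser or vitrectomy.

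Cost: SAP wording, one derivation and one sensitivity run. A few observed responders become non-responders, at about 1 to 3 points of power at 35% v 10% in the assumed cases.

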6.3 Measures to minimize bias: Randomization and masking

All participants will be centrally assigned to randomized study intervention using IWRS. Before the study is initiated, the log in information and directions for the IWRS will be provided to each site.

Participants will be randomized to either Placebo or Runcaciguat. Randomization will be stratified by baseline DRSS score (47 or 53). In Part 1, the randomization ratio will be 2:1 runcaciguat: placebo and in Part 2 it will be 1:1.

Potential bias will be reduced by the use of central randomization via the IWRS. The level of masking is presented in Table 6-2.

Table 6-2	Level of masking – Part 1 and 2

	Masked	Unmasked
Participant	•	
Care provider	•	
Investigator	•	
Outcomes assessor	•	
Sponsor study team (except Bioanalytical / PK group)	•	
Sponsor Bioanalytical / PK group		•

PK = pharmacokinetics

The IWRS will be programmed with instructions on how to break / unmask a participant's randomized treatment. In case of an emergency, the investigator has the responsibility for determining if unmasking of a participant's intervention assignment is warranted. If the investigator is unavailable, and a treating physician not associated with the study requests emergency unmasking, the emergency unmasking requests are forwarded to the emergency medical advice 24 hours / 7 day service. Participant safety must always be the first

09 FEB 2023 Page: 40 of 95

consideration in making such a determination. If the investigator decides that unmasking is warranted, the investigator should make every effort to contact the sponsor prior to unmasking a participant's intervention assignment unless this could delay emergency treatment of the participant. If a participant's intervention assignment is unmasked, the sponsor must be notified within 24 hours after the unmasking. Date and reason for the unmasking must be recorded in the source documentation and case report form, as applicable.

Bioanalytics and pharmacometrics staff will be unmasked according to Sponsor's standard operating procedures. Pharmacometrics analysis and report will be done under a separate cover. Bioanalysis and pharmacometrics evaluation might be started prior to database lock: if this is applicable, appropriate measures will be taken to maintain masking of the study team, e.g. data will be stored separately, and members of the study team will not have access to the unmasked data.

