Participants are randomly assigned to one of two study arms. Randomization will be done stratified by baseline DRSS (47 or 53). A combined total of approximately 98 participants for Part 1 and 2 will be randomly assigned for an estimated total of  $\geq$  40 participants per intervention group evaluable for primary endpoint assessment.

During the initial 4 weeks, treatment will be titrated to the target dose of 120 mg runcaciguat or matching placebo. Treatment will continue at the highest tolerated dose until completion of 48 weeks of treatment if tolerated, or until development of a VTC or development of PDR.

An EoS visit will be performed 4 weeks after EoT. This includes both participants who complete the planned treatment period, and participants who discontinue treatment early including treatment discontinuation due to VTC.

The study population is characterized by the following main inclusion criteria:

- Age  $\geq 18$  years
- Moderately severe to severe NPDR in the study eye: DRSS levels 47 or 53
- Diabetes type 1 or 2

- BCVA ETDRS letter score in the study eye of  $\geq$  69 letters (approximate Snellen equivalent of 20/40 or better)
- Refraction with a spherical equivalent from -6 dpt to +5 dpt

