The response criterion is assumed to be binomially distributed within each treatment arm. For the Bayesian evaluation, a Jeffrey's prior (i.e., a Beta (0.5,0.5)-prior) will be used. Under these assumptions, the posterior distribution for the parameter  $\pi$  will be a Beta (k+0.5, n-k+0.5)-distribution, where

- k is the number of patients with DRSS  $\geq$  2-step improvement within the respective study arm and
- n is the number of patients within the respective study arms.

In order to demonstrate the clinical activity, the posterior distribution of  $\pi_{ACT} - \pi_{PLC}$  will be used to establish the posterior probability that  $\pi_{ACT} - \pi_{PLC} > 0$  by using a Monte-Carlo-approach.

The posterior distribution for clinical relevance can be directly evaluated from the Beta (k+0.5, n-k+0.5)-distribution in the runcaciguat arm.

The Bayesian posterior probabilities  $P(\pi_{ACT} - \pi_{PLC} > 0 | data)$  and  $P(\pi_{ACT} > 0.25 | data)$  will be calculated using a Monte Carlo Approach: Within each arm, 100000 samples will be obtained from the posterior distribution (i.e., a Beta (k+0.5, n-k+0.5)-distribution). As a seed for random number generation, a fixed seed will be used. This seed has to be included into the program output, in order to ensure that the analysis can be repeated.

From these random samples, the following quantities will be obtained:

- Estimation of  $P(\pi_{ACT} \pi_{PLC} > 0 | data)$ :
  - Difference  $\delta^{(i)}$  between the ith sampled proportion in the active arm  $(=\pi_{ACT}^{(i)})$  and the ith sampled proportion in the placebo arm  $(=\pi_{PLC}^{(i)})$ :  $\delta^{(i)} = \pi_{ACT}^{(i)} - \pi_{PLC}^{(i)}$
  - Relative frequency of the event ' $\delta^{(i)} > 0$ ' within the samples of  $\delta^{(i)}$
- Estimation of  $P(\pi_{ACT} > 0.25 | data)$ :
  - Relative frequency of the event ' $\pi_{ACT}^{(i)} > 0.25$ ' within the samples of  $\pi_{ACT}^{(i)}$

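### Randomisation is stratified by baseline DRSS (47 or 53), but the proof-of-concept posterior in SAP 4.2.2 pools the strata and no stratum-adjusted version of the decision is planned

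*SAP*

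**What the plan says.** Baseline DRSS is the only stratification factor (Protocol 6.3: "Randomization will be stratified by baseline DRSS score (47 or 53"). SAP 1.2 says the same. Allocation differs by study part: "In Part 1, the randomization ratio will be 2:1 runcaciguat: placebo and in Part 2 it will be 1:1". The plan is 52 runcaciguat and 46 placebo randomised, falling to about 80 evaluable (Protocol 9.2, SAP 5).

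The deciding analysis is in SAP 4.2.2, on the compliant participants of the per protocol set (PPS). It has no stratum term: "The response criterion is assumed to be binomially distributed within each treatment arm". Each arm gets a Beta(k+0.5, n−k+0.5) posterior. PoC requires a posterior probability of at least 0.90 that π_ACT exceeds π_PLC, and of at least 0.50 that π_ACT exceeds 0.25. Protocol 9.4.2 has the same model, and the repeat on the full analysis set (FAS) uses the same pooled rule.

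The stratum appears elsewhere:
- In SAP 4.2.3 the imputation model for missing responses is fitted "with stratum (baseline DRSS) and treatment group as effects". The completed data sets then go back into the pooled posterior.
- In SAP 4.2.4 levels 47 and 53 are optional subgroups, on the stated ground that such characteristics may influence the primary endpoint.
- In SAP 6.2 study-eye DRSS is tabulated by arm in the FAS and PPS. It also orders listings and plots.

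**The concern.** A two-step improvement is a different task in each stratum: on the scale in SAP 6.6 it means 53 to 43, or 47 to 35. If response differs by baseline level, a single binomial per arm mis-states the design in two ways.

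- **Strata balanced.** Stratified randomisation has removed the between-stratum variance from the comparison, but the pooled posterior still counts it. The posterior is then somewhat too wide.
- **Strata unbalanced.** Balance is arranged at randomisation, whereas the decision is taken on the PPS after losses. If the level-53 share then differs between arms, the pooled difference carries the gap in stratum share multiplied by the gap in response.

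The decision is a fixed cut-off on about 80 people, so a chance shift of this kind can move a trial across the line in either direction. The factor that would correct it is already recorded for everyone.

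**Working it through.** **Inputs from the documents:** 40 evaluable per arm; true rates 10% placebo and 35% runcaciguat; Beta(0.5, 0.5) prior; cut-offs 0.90 and 0.50; 52/46 randomised, about 80 evaluable.

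**Assumed, because the documents are silent:** half the participants at level 53, and the response rates by stratum. Rates are written level 47/level 53. Counts such as 22 v 20 are level-53 participants of 40, runcaciguat v placebo.

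**1. The plan's own figure.** I enumerated all outcomes (k_ACT, k_PLC) at 40/40, with independent Beta(k+0.5, 40−k+0.5) posteriors and both criteria applied. Activity is met with probability 93.6% and PoC with probability 90.3%. The stated value of at least 90% reproduces.

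**2. Balanced strata, no drug effect.** The variance of k in one arm shows the direction.
- 10%/40%: the true variance is 20×0.1×0.9 + 20×0.4×0.6 = 6.6. The pooled binomial at 25% assumes 40×0.25×0.75 = 7.5.
- 5%/15%: the true variance is 20×0.05×0.95 + 20×0.15×0.85 = 3.5, against 40×0.10×0.90 = 3.6.

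The pooled rule is therefore mildly conservative when strata differ strongly, and hardly at all when they differ by 10 points. Exact enumeration gives false PoC of 8.3% at 10%/40%, against 9.6% if both strata respond at 25%.

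**3. Unbalanced strata, no drug effect, 10%/40%.** The pooled difference is shifted by (gap in level-53 share) × (0.40 − 0.10).

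| Level-53 count | Shift in difference | Pooled false PoC |
|---|---|---|
| 20 v 20 | 0 | 8.3% |
| 22 v 20 | 0.05×0.30 = 1.5 points | 11.1% |
| 24 v 20 | 0.10×0.30 = 3.0 points | 14.4% |
| 18 v 22 | −0.10×0.30 = −3.0 points | 4.4% |

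**4. How often such gaps arise.** Start from balanced strata (26 of 52 and 23 of 46) and lose 18 of 98 at random. The gap in stratum share is at least 5 points in about 34–36% of trials, and at least 10 points, in either direction, in about 5%.

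**5. Average over random loss** (52 to 40 and 46 to 40). The false-activity rate of the pooled rule is 10.2% for 5%/15% strata, 9.5% for 15%/35% and 8.8% for 10%/40%. With homogeneous strata it is 10.5% at a 10% rate and 10.0% at 25%. The average is not raised.

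**6. At the planning placebo rate.** With 5%/15% strata, averaging 10%, balanced false activity is 10.2%. False PoC is 0.4% when balanced and at most 0.8% even at 24 v 16. The relevance criterion blocks it.

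**7. A true effect.** Take 20%/50% on runcaciguat and 5%/15% on placebo, which average the planned 35% and 10%. At 18 v 22 the expected pooled rates are (22×0.20 + 18×0.50)/40 = 33.5% and (18×0.05 + 22×0.15)/40 = 10.5%. The expected difference is 23.0 points instead of 25. P(PoC) falls from 91.4% when balanced to 87.3%; the stratified rule gives about 90% in the same samples.

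**8. The stratified rule.** Use Beta(k+0.5, n−k+0.5) in each arm-by-stratum cell, weighted by the pooled stratum shares (20,000 simulated trials per case, Monte Carlo standard error about 0.2 points). False PoC is about 9.4–10.5% across the 10%/40%, 15%/35% and 25%/25% cases, with imbalances up to 24 v 16 in either direction examined for the first two. At the planning rates with balanced strata, P(PoC) is about 90.4–90.6%, against 90.3% pooled.

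**The case against.** The strongest reply is that nothing stated in the plan is violated. PoC is defined by posterior probabilities, no type I error rate is given, and the one stated operating characteristic reproduces. This stands: 10% is only what a 0.90 cut-off roughly implies.

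A reader might infer that pooling inflates the trial's error rate. The documents do not support that. Under losses unrelated to arm and stratum the average is at or slightly below the homogeneous value. A net inflation would need exclusions that differ by arm within stratum, which the documents neither show nor rule out. Nor is the rule always too strict when strata balance: at 5%/15% false activity is 10.2%.

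A reader might also point to extreme imbalance. At 24 v 16 with 10%/40% strata, pooled false PoC would be 23.4%, and 2.1% with the arms reversed. But a 20-point gap has probability of only about 0.00002 under the random-loss model, so it is no guide to this trial. The 10%/40% null also implies 25% placebo response, well above the planned 10%.

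Some of the gap is already covered. SAP 6.2 will show any PPS imbalance, the FAS repeat removes the compliance exclusions, and the subgroup results may be produced. None of these gives an adjusted PoC decision, and the subgroup analyses are optional. The SAP 3 wording against further stratification concerns study parts, not DRSS.

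**Conclusion.** The omission is real and its consequence is modest. The plan stratifies on a factor that it says may influence response, then leaves that factor out of the posterior that decides PoC, with no adjusted version alongside.

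The effect is conditional on the sample obtained. It needs a strong stratum effect together with a chance imbalance in the PPS. On the assumed 10%/40% rates, false PoC moves from 8.3% to 11.1% or 14.4% for gaps of 5 or 10 points towards runcaciguat. On the assumed 20%/50% v 5%/15% rates, a 10-point gap the other way lowers P(PoC) to 87.3%. At the planning placebo rate the effect on false PoC is negligible. The average error rate and the stated 90% probability of PoC are not in question. All sizes depend on stratum rates and a stratum mix that the documents do not give.

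The case for acting is that the design and the analysis should match and the change costs very little, not that the planned decision is unsound.

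**What to change.** In SAP 4.2.2, before unmasking:
1. Sample from Beta(k+0.5, n−k+0.5) in each of the four arm-by-baseline-DRSS cells.
2. Form π_ACT and π_PLC as sums over strata, weighted by the stratum shares in both arms combined.
3. Apply both PoC criteria to these standardised rates, and keep the pooled posterior as a supportive analysis.

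The minimum alternative is to leave the pooled rule as primary and pre-specify the stratified version as a sensitivity analysis of the PoC decision, read beside the PPS stratum table that SAP 6.2 already provides.

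**Cost.** SAP wording and a few program lines. The prior weighs two participants per arm instead of one. Average power hardly changes. If the strata turn out not to matter and are unbalanced at 18 v 22 or 22 v 18, P(PoC) at the planning rates is about 89.4–89.5% stratified, against 90.3% pooled. Splitting the prior into Beta(0.25, 0.25) cells would keep its weight at one participant per arm, but false PoC rises to about 11% when both strata respond at 25%. The plan's own Beta(0.5, 0.5) in each cell is preferable.
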